YMSM and YTGW. We will be including BOTH YMSM who have sex with men and YTGW who have sex with men. We believe that targeting of those youth most at-risk of acquiring HIV is the most efficient strategy for implementation in practice. Based on the research to date, barriers to HIV testing for YMSM and YTGW have significant overlap,^{114, 115} suggesting that the mLab App which seeks to overcome these barriers is likely to increase HIV testing uptake in both groups. Nevertheless, we will test potential differences in intervention response by race/ethnicity, sexual and gender minority status (i.e., YMSM vs. YTGW), and co-morbid conditions (i.e., depression and anxiety symptoms, history of trauma) in order to inform future tailoring or targeting of the mLab App.

Settings. This will be a multi-site study in NYC and Chicago. NYC, NY ([name], MPI).¹¹⁶ In 2013, there were 117,618 persons living with HIV in NYC. Of these, 43,940 (over 37%) were infected through male to male sexual contact. Our main recruitment site will be through the Columbia University Medical Center Community Partnership for Health. In addition, we have a number of close community partners in NYC from where we will be recruiting. We work closely the LGBT Center in lower Manhattan and Ali Forney, which provides services for homeless young MSM and TGW and particularly Black and Latino youth. Chicago, IL ([name], MPI). The 2013 rate of HIV infection diagnoses in Chicago (40.4 per 100,000) is approximately 2.5 times higher than the national rate, and the prevalence rate for Chicago (827.9/100,000) is nearly 3 times the national rate. Our main recruitment site will be through The Center for Gender, Sexuality and HIV Prevention at Lurie Children's Hospital within the Division of Adolescent Medicine, directed by [name]. Additionally, we will advertise the study to the entire hospital system in the Chicago area to recruit youth and collaborate with community partners who serve youth.

All of our study activities will be conducted in a private conference room at the Columbia University School of Nursing or at the Lurie Children's Hospital.

Sample. We will recruit 20 youth from both Chicago and NYC to participate in the evaluation of the mLab App interface screens. According to Faulkner,¹¹⁷ 20 users are sufficient to identify 99% of usability problems. Each participant will be given \$40 for participating in the usability evaluation, which is expected to take 60-90 minutes.

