Sample. Our sample will include 525 Black, Latino, and other young men and transgender women (inclusive of YMSM and YTGW aged 18-29 years), with Chicago: N=180 and New York: N =345; representing the population size of each city.¹²⁸ **Statistical power and sample size calculation.** This study will use a 2:2:1 RCT design. We plan to recruit total 525 subjects (210, 210, and 105 will be in arm 1, 2, and 3, respectively). The power and sample size calculations are based on the comparison of HIV testing rates in the mLab App arm compared to the standard of care HIV information control arm for Hypothesis 1 (i.e., compare HIV testing at 6 months and re-testing during 7 to 12 months). We calculated the statistical power to detect a difference across all participants (YMSM and YTGW). Our study is not powered to detect differences in outcomes in YMSM and YTGW separately but we will analyze differences in effect by gender identity (see Data Analysis Section below). The effect size is calculated based on the findings from the FORTH RCT⁷⁵ in which self-testing resulted in a two times increase in frequency of HIV testing in high-risk MSM, and a nearly four times increase in non-recent testers compared with standard care, without reducing the frequency of facility-based HIV testing. Using a Poisson distribution, we estimated a 40% HIV testing rate over 6 months for the control group and approximately 60% HIV testing rate for the intervention group. We are using a more conservative effect size than the one **reported** previously by assuming 60% testing rate for the intervention as compared to 85% in the FORTH RCT study.⁷⁵ This 20% difference is equivalent to a medium effect size. All power calculations are based on alpha=0.05 and two-sided tests of the primary comparison and an attrition rate of 20% at 6 and 12 months. We will have at least 80% power for Hypothesis 1, to conduct two tests simultaneously (i.e., to compare HIV testing rate during the first 6 months and to compare re-testing rate during 7 to 12 months).

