All multivariate analyses will be preceded by standard descriptive bivariate analyses to describe the key variables and relationships among them. These analyses will include means, frequency tables, histograms, and examination of distributions. Frequencies and rates of HIV tests, as well as corresponding confidence intervals, will be calculated for each arm. All statistical tests will be two-sided tests with the level of significance at 0.05. Hypotheses testing will be based on logistics models to compare (1) HIV testing during the first 6 months; and (2) HIV re-testing at 7-12 months between the mLab App arm and the control (*Hypothesis 1*). We will conduct stratified analyses to examine the differences in testing uptake in subgroups (i.e., racial/ethnic, age, YMSM vs. YTGW, and risk level). Effect sizes will also be compared between arms 1 and 3 to describe differences in testing and linkage behavior attributable to the mLab app with home test distribution versus home test distribution only. Linkage to care will be measured by the percent of study participants who tested positive and

attended a first HIV care appointment at NYP/Columbia or Lurie or who provide documentation of care at another clinic and the time to link to care after positive result. Follow-up surveys for HIV positive participants will also include questions regarding positive diagnosis, such as disclosure and seeking care. For participants who test HIV positive, we will compare the rates of linkage to care between the mLab App arm and the control arm using Fisher's exact test (*Hypothesis 2*). However, because the number of positive (HIV) tests is expected to be approximately 25-40, this part of the study will not have power to detect a significant statistical difference between groups.

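### The plan promises to test whether the app's effect differs by subgroup, but its analysis section names only stratified analyses, which on their own do not test that

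*Combined protocol and SAP*

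**What the plan says.** Three places bear on this.

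- The paragraph headed YMSM and YTGW, which sits under the Aim 1 end-user evaluation but speaks about intervention response, states that "we will test potential differences in intervention response by race/ethnicity, sexual and gender minority status". It adds co-morbid conditions (symptoms of depression and anxiety, and trauma history). The purpose given is "in order to inform future tailoring or targeting of the mLab App".
- The Aim 2 paragraph on statistical power and sample size says "we will analyze differences in effect by gender identity" and sends the reader to the Data Analysis section for this. The same sentence carries a caveat: "Our study is not powered to detect differences in outcomes in YMSM and YTGW separately".
- The Aim 2 Data Analysis section, under Analysis of Intervention Effects, says of the main comparison that "Hypotheses testing will be based on logistics models", arm 1 against arm 2, and sets a two-sided 0.05 level for all tests. On subgroups it says only "We will conduct stratified analyses to examine the differences in testing uptake in subgroups", with the factors given as "i.e., racial/ethnic, age, YMSM vs. YTGW, and risk level".

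No interaction term, homogeneity test, rule for declaring that effects differ, or multiplicity rule for subgroups appears in the documents. The two factor lists also differ. The Data Analysis section has age and risk level, which the earlier paragraph lacks. The earlier paragraph has co-morbid conditions, which the Data Analysis section lacks.

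**The concern.** The question asked is whether the effect of the app differs between groups. That is a question about a difference between two effects, and it needs an estimate of that difference with its own standard error. Separate analyses by stratum supply the two effects but not the comparison. The power paragraph points forward to a section that contains no method for what it promises.

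Without a stated comparison, the result most readily to hand is a set of within-stratum estimates, some significant and some not. Significance within a stratum depends heavily on its size. If the transgender women are the smaller stratum, a non-significant result there could be taken as a sign that the app does not work for them, when the effect is the same and only the numbers differ. Because the results are meant to guide tailoring or targeting, that misreading could have consequences.

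**Working it through.** **Inputs from the documents** (Aim 2 power paragraph): 210 per arm in arms 1 and 2; 20% attrition, so 210 × 0.8 = 168 completers per arm; testing rates of 40% and 60%; two-sided alpha 0.05. **Assumed, because the documents do not give them:** subgroup shares, taken as equal in both arms, and a common true effect in every stratum.

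**Step 1. The plan's own figure.** With n per arm, p1 = 0.4, p2 = 0.6 and pooled p = 0.5:

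power = Φ[(0.2√n − 1.96√(2 × 0.5 × 0.5)) / √(0.4 × 0.6 + 0.6 × 0.4)]

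At n = 168 this is Φ[(2.592 − 1.386) / 0.693] = Φ(1.741) = 0.959. Both Hypothesis 1 tests succeed with probability about 0.959² = 0.92 if independent. At 0.025 each, power is 0.927 per test and about 0.86 for both. The stated minimum of 80% is met.

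**Step 2. Separate significance when the effect is identical.** Divide the 168 per arm between two strata, and let a and b be the stratum powers from the same formula. Then P(exactly one significant) = a(1 − b) + b(1 − a).

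| Assumed split | Completers per arm | a, b | Exactly one significant |
|---|---|---|---|
| 50:50 | 84, 84 | 0.741, 0.741 | 0.384 |
| 60:40 | 100.8, 67.2 | 0.815, 0.643 | 0.410 |
| 70:30 | 117.6, 50.4 | 0.871, 0.520 | 0.486 |
| 80:20 | 134.4, 33.6 | 0.911, 0.372 | 0.605 |
| 90:10 | 151.2, 16.8 | 0.939, 0.207 | 0.758 |

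For 80:20, as an example: 0.911 × 0.628 + 0.372 × 0.089 = 0.572 + 0.033 = 0.605. A simulation of 5,000 trials using Wald tests of the stratum log odds ratios agrees: 0.39 to 0.40 at 50:50, 0.48 to 0.50 at 70:30, and 0.77 at 90:10.

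The figures depend on the true effect. For splits of 50:50, 70:30 and 90:10 they are:

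- 40% versus 50%: 0.379, 0.392, 0.430
- 40% versus 55%: 0.500, 0.548, 0.679
- 40% versus 65%: 0.168, 0.295, 0.698

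**Step 3. The interaction test under the same common effect.** It compares the two log odds ratios directly: z = (logOR1 − logOR2) / √(var1 + var2). In the simulations it declared a difference in 4.5% to 5.5% of trials per factor, as its nominal level implies. Across four independent two-level factors, at least one false declaration occurs in 1 − 0.95⁴ = 18.5% of trials (simulated 18% to 19%).

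**Step 4. What the interaction test can detect.** Suppose one stratum has 40% versus 60% (odds ratio 2.25) and the other 40% versus 40% (odds ratio 1). The difference is ln 2.25 = 0.811. Each arm of a stratum with m completers contributes variance 1/(m × 0.24). At 50:50, SE = √(4 / (84 × 0.24)) = 0.445, so z = 1.82 and power is Φ(1.82 − 1.96) ≈ 0.445. At 70:30 power is 0.385, and at 90:10 it is 0.194.

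**The case against.** The strongest reply is that the protocol does intend a comparison of effects. It says so twice, and the term stratified analyses does not exclude a homogeneity test across strata. A reader might infer that the plan is to declare a difference whenever one stratum is significant and another is not. The documents do not say this. The stratified-analysis sentence mentions no p-value, and the 0.05 level is a general rule for all tests. The defect is a promised test with no method, not a declared plan to compare p-values.

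A reader might also infer that a spurious one-group-only pattern would be the usual outcome. For a single two-level factor under the planned effect, the table does not support that: the chance stays below half for splits from 50:50 to 70:30.

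The power caveat for YMSM and YTGW also counts in the plan's favour, as does a purpose worded in terms of future tailoring, which is close to hypothesis-generating. An interaction test would itself often be inconclusive here.

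All of this stands, and it limits the size of the point. It does not supply the missing method. The statement of aim is in one place, the section it depends on names an analysis that does not answer the question, and the caveat does not say how subgroup results will be compared. Low interaction power is a reason to report the interaction with its interval and to label it exploratory. Separate stratum results do not get round it.

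**Conclusion.** The concern holds as a mismatch between the stated question and the named method. The plan undertakes to test or analyse differing effects, and the only subgroup method given does not compare effects. How often this could mislead is conditional. It applies only if the strata are read by their separate significance, and it ranges from about 38% to 76% of trials over splits from 50:50 to 90:10, given a common 40% versus 60% effect and 168 completers per arm. The corresponding false-declaration rate for an interaction test is about 5% per factor. The splits are assumed, and the across-factor figure also assumes independent factors. Hypothesis 1 and its sample size are unaffected.

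**What to change.** In the Aim 2 Data Analysis section:

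- For each subgroup factor, add an arm-by-factor interaction to the logistic model for arm 1 versus arm 2.
- Report the interaction estimate, 95% confidence interval and p-value, with the subgroup-specific effect estimates and their intervals alongside.
- State that no conclusion about differing effects will be drawn from within-stratum p-values.
- Label these analyses exploratory and say that interaction power is low: about 19% to 45% even if one stratum has no effect at all. This fits the caveat already in the power paragraph.
- Reconcile the factor lists, so that age, risk level and co-morbid conditions are each either included in both places or dropped from both.

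The cost is a few sentences of analysis-plan wording. The change needs no more participants and leaves the primary analysis as it is. Any co-morbid condition that is kept must be among the variables collected at baseline.

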
Aim 1: Refine the user interface of the mLab App – a mobile and connected health intervention for increasing the uptake of rapid home HIV self-testing (OraQuick) and linkage to care – by employing rapid cycle iterative design methods with feedback from human computer interaction experts (N=5), end-users (N=20), and youth advisory board members (N=10).

Aim 2: Evaluate the efficacy of the mLab App in improving both HIV testing rates and linkage to care versus standard preventive care in 525 Black, Latino and other young men and transgender women (inclusive of YMSM and YTGW age 18-29 years) in a 12-month multi-site trial, with randomization to three groups (intervention, standard of care-HIV information control arm, HIV home tests) at each site.

Hypothesis 1. Youth randomized to the mLab App arm (arm 1), as compared to youth in the standard of care HIV information control arm, will have: a) increased rates of HIV testing within the first 6 months of the trial; and b) increased rates of re-testing in months 7-12 of the trial.

Hypothesis 2. The total number of youth who test HIV positive and link to care in the **mLab App** arm will be greater as compared to the standard of care HIV information control arm.

Hypothesis 3. The image processing in the **mLab App** will: 1) have no statistically significant difference in sensitivity or specificity when compared to confirmatory testing, 2) have greater sensitivity and specificity when compared to the user-submitted self-analyses.

Aim 3: Monitor and analyze paradata to understand the effect of user engagement of the **mLab App** on improving HIV testing rates and linkage to care.

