Step 3. Review with YAB. Drs. [name] and [name] will facilitate the review of the mLab App user interface, content, and function with the YAB. Through our review, we will ensure that the mLab App is culturally appropriate for both YMSM and YTGW. [name] will insert changes directly into the mLab App mock-ups viewed on a screen, supplemented by note-taking by study staff and audio-recorded. This allows us to confirm meaning, make revisions as necessary, and reach consensus with the YAB. [name] will probe for further discussion on feasible ways forward and to ensure that the mLab App meets the current prevention guidelines. We will incorporate the recommended changes. As a final step, we will have members of the YAB test the final mLab App after the meeting in their own settings (e.g., Home) and return any comments or additional edits within 2 weeks. Final recommendations for the user interface will be shared with [name], who will work with his team and the graphic design team at Little Green Software (see letter of support) to make the final updates to the app.

Aim 2: Evaluate the efficacy of the mLab App in improving both HIV testing rates and linkage to care versus standard preventive care in 525 Black, Latino and other young men and transgender women (inclusive of YMSM and YTGW age 18-29 years) in a 12-month multi-site trial, with randomization at each site to three groups arm 1: intervention (mLab App) (N=210); arm 2: standard of care HIV information control arm (N=210); arm 3: OraQuick home test kits only (N=105).

Hypothesis 1. Youth randomized to the mLab App arm, as compared to youth in the standard of care HIV information control arm, will have: a) increased rates of HIV testing within the first 6 months of the trial; and b) increased rates of re-testing in months 7-12 of the trial.

Hypothesis 2. The total number of youth who test HIV positive and link to care in the mLab App arm will be greater as compared to the standard of care HIV information control arm.

Hypothesis 3. The image processing in the mLab App will: 1) have no statistically significant difference in sensitivity or specificity when compared to confirmatory testing, 2) have greater sensitivity and specificity when compared to the user-submitted self-analyses.

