Eligibility criteria. In addition to the eligibility criteria listed in Aim 1 – End-User Usability Testing, we will also include the following eligibility criteria: 1) understand the limitations of the OraQuick test and the mLab App (e.g., a confirmatory test is needed – see Protection of Human Subjects); 2) not having been tested for HIV in the past 6 months (e.g., therefore being somewhat outside of the current CDC testing recommendations for high-risk populations – see below). 3) not currently taking PrEP and 4) receive a non-reactive result on the rapid HIV test at the baseline visit

Alternatives and Potential Limitations. *We carefully considered the frequency of testing for our study participants and have agreed that participants should test at least every 3-6 months based on the following 2 considerations:* 1) Current CDC guidelines recommend annual testing and more frequent (every 3-6 months) for sexually active MSM at high-risk for HIV infection based on individual risk factors.^{129, 130} 2) Since all of our participants meet the criteria for use of PrEP¹⁰⁷ and based on our clinical experience for interpretation of these guidelines, we have specified that our study participants should test a minimum of every 3-6 months.^{27,28} As part of the intervention, participants in arm 1 will be reminded to use the OraQuick tests at 3 month, 6 month, 9 month, and 12 month time points through the mLab app.

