Missing Data. Multiple imputation (MI) methods will be applied to address missing values under the missing at random (MAR) assumption (i.e., missingness can be fully accounted for by variables with complete information).¹⁴¹ These analyses will be complemented with assessment of how sensitive the inferences are to the MAR assumptions. Sensitivity analysis will be performed based on selection models for dropout.¹⁴²⁻¹⁴⁴ Intention-to-Treat (ITT) Analysis: All analyses will use the ITT principle,¹⁴⁵ which requires subjects' data to be analyzed as randomized, regardless of whether they used the mLab App or not.

Aim 3: Monitor and analyze paradata to understand the effect of user engagement of the mLab App on improving HIV testing rates and linkage to care.

To understand barriers and/or facilitators of its use, the mLab app will automatically collect paradata for each user interaction throughout the study. This paradata is considered "free" in that it does not require any additional effort from the user.¹⁴⁶ This data will be analyzed for each user, as well as aggregated to understand what component of the intervention lead to behavior change. We will specifically examine who uses the mLab App and how frequently it is used over time.

Methods. We will capitalize on the use of the extant mLab software which is written as a mobile-friendly web application in hypertext markup language (HTML), hypertext preprocessor (PHP), JavaScript, and Python (for computer vision), and integrates with REDCap for backend data storage. On each page of the mLab app, a PHP script logs every user interaction before the page of the application is displayed to the user. Therefore, any event that would refresh or send the user to a new page (e.g., HTML links) initiates an event-driven paradata capture. The PHP script transmits the data to REDCap through the secure REDCap API.

Data Analysis. The primary paradata that will be collected is shown in Table 4. From this data, we will derive the following use data for each session: duration on each page, page progression through the application, time from login to result, number of rapid test pictures previewed before sent for result, and total time prior to logout. We will analyze the data on multiple scales and perspectives: individual-level (i.e. user-level), application-level, page-level, session-level, and how these differ by demographic characteristics, HIV testing history, technology

Table. Paradata Collected for Each mLab Event

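### Hypothesis 2 is about how many youth test HIV positive and link to care, but its only test compares linkage among those who test positive, so extra case-finding cannot count

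*Combined protocol and SAP*

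**What the plan says.** The hypothesis appears under Study Aims and again under Aim 2: "The total number of youth who test HIV positive and link to care in the mLab App arm will be greater" than in the standard-of-care information arm. It concerns a joint outcome, testing positive and then linking, counted over the whole arm.

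The only test labelled Hypothesis 2 is in Data Analysis: "For participants who test HIV positive, we will compare the rates of linkage to care between the mLab App arm and the control arm". The method named is Fisher's exact test. The same paragraph expects about 25 to 40 positive tests and says this part of the study will lack power.

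Just before that, the measure is introduced: "Linkage to care will be measured by the percent of study participants who tested positive and". The rest of that sentence defines linkage as a first visit for HIV care at a study clinic, or documented care elsewhere. The denominator of that percentage is unclear. It could be all participants or those who tested positive.

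Three other places bear on the point:

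- Eligibility criteria require that participants "receive a non-reactive result on the rapid HIV test at the baseline visit".
- The sample size section states: "we estimated a 40% HIV testing rate over 6 months for the control group and approximately 60% HIV testing rate for the intervention group".
- The ITT paragraph requires "data to be analyzed as randomized, regardless of whether they used the mLab App or not".

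**The concern.** The joint outcome can rise in two ways: the app can uncover more infections, or it can link a larger share of those uncovered. The planned test sees only the second. Case-finding is the route the plan relies on most, since the power calculation is built on the app raising testing.

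Because all participants start non-reactive, testing positive happens after randomisation and depends on how much each arm tests. The positives in arm 1 and those in arm 2 may differ in ways randomisation did not balance, even though each person stays in the assigned arm.

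Two consequences follow. A non-significant result could be reported as no support for Hypothesis 2 when that hypothesis was not tested. The observed comparison could also point towards control while more app-arm youth are in care.

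**Working it through.** **Inputs from the plan.** 210 randomised in each of arms 1 and 2, 525 in all; testing 60% against 40%; 25 to 40 positive tests; two-sided 0.05; Fisher's exact test. The plan gives no HIV incidence, so the 25 to 40 cannot be reproduced, and it does not say which arms that figure covers. If it covers all three arms, a pro rata share for arms 1 and 2 is 25 × 420/525 = 20 to 40 × 420/525 = 32. If it covers arms 1 and 2 only, it stays 25 to 40. I use 20 to 40.

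**Assumptions.** The plan gives no linkage rate, so I take 80% to 90%, equal in both arms. I assume equal infection risk. Positives proportional to testing split 0.60/0.40 = 1.5:1. As a less favourable case, suppose infections are spread evenly over 12 months and testing falls at the end of each half-year. The share detected is then (0.84 + 0.60)/2 = 0.72 in the app arm and (0.64 + 0.40)/2 = 0.52 in control, a ratio of 1.385:1.

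**Step 1: the two quantities.** For each arm,

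P(positive and linked) = P(positive) × P(linked given positive).

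Hypothesis 2 concerns the left side. The planned test compares the last factor only. With equal linkage and a 1.5:1 split, the left side differs by 1.5 × 1 = 1.5, while the last factor does not differ. More participants could not lift the planned test's rejection rate above 5%.

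**Step 2: one worked case.** 32 positives at 1.5:1 are about 19 and 13. At 80% linkage about 15 and 10 link.

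- As planned: 15/19 against 10/13, p = 1.0.
- All randomised: 15/210 (7.1%) against 10/210 (4.8%), p = 0.41.

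**Step 3: direction.** Take 15 and 10 positives (1.5:1), with 11 and 9 linked.

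- As planned: 11/15 (73%) against 9/10 (90%), favours control, p = 0.61.
- All randomised: 11/210 (5.2%) against 9/210 (4.3%), favours the app, p = 0.82.

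Neither is significant. The example shows only that the two comparisons can disagree in sign.

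**Step 4: rejection rates.** Positives in each arm are binomial out of 210, and linked participants are binomial among positives with the same rate in both arms. Summing the probability of every outcome with Fisher p ≤ 0.05 gives:

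| Positives, arms 1+2 | Linkage (both arms) | Planned test, 1.5:1 | All randomised, 1.5:1 | All randomised, 1.385:1 |
|---|---|---|---|---|
| 20 | 80% | 1.6% | 8% | 6% |
| 20 | 90% | 0.6% | 9% | 7% |
| 32 | 80% | 2.4% | 13% | 9% |
| 32 | 90% | 1.2% | 15% | 11% |
| 40 | 80% | 2.8% | 17% | 12% |
| 40 | 90% | 1.6% | 19% | 13% |

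The planned test's rates at 1.385:1 are the same to within 0.1 point.

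**The case against.** The strongest reply is that little turns on this. Hypothesis 2 is not the primary outcome, the plan openly says it lacks power, and at the plan's own testing ratio both analyses are likely to be non-significant. The linked count per arm could also be read from the planned table. All of that stands and limits the weight of the point. It does not answer it: the plan discloses few events, not that the test addresses another quantity, and a count read off a table has no pre-specified estimate, interval or test.

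A second reply is that the linkage-measure sentence may already mean all participants. It may, but the test sentence restricts the comparison to those who test positive, so the two must be reconciled.

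A third reply is that the all-randomised outcome has its own weakness. In arm 1, results and images reach the team through the app. In arm 2, positives and linkage come to light through surveys, clinic attendance or documents that participants supply. Capture may therefore be more complete in arm 1, and the fix must allow for that.

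Two stronger readings are tempting. A reader might infer that the planned test breaches the plan's ITT rule. It does not: that rule asks for analysis by assigned arm regardless of app use, and the Fisher test keeps people in their assigned arms. The loss of randomisation's protection among positives is a separate matter. A reader might also infer that the right denominator would turn a null result into a significant one. That needs a far more uneven split of positives than 1.5:1, and nothing in the documents supports one.

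**Conclusion.** The concern holds. The test labelled Hypothesis 2 does not test Hypothesis 2, and the text nearby leaves the denominator of the linkage measure open. Under equal linkage the planned test rejects in about 0.6% to 2.8% of trials however true the hypothesis is. The matching analysis has about 8% to 19% power at 1.5:1 and about 6% to 13% at 1.385:1. These ranges rest on 20 to 40 positives in arms 1 and 2, equal infection risk and assumed linkage of 80% to 90%. The mismatch itself rests on the wording alone.

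The plan should be changed, but the gain is modest: an estimate and a test of the stated hypothesis, not a decisive result.

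**What to change.** 1. For Hypothesis 2, compare the proportion of all randomised participants in arms 1 and 2 (210 against 210) who test HIV positive and link to care within 12 months. Report the risk difference with a 95% CI and Fisher's exact test. Count as linked only those who meet the plan's existing attendance-or-documentation definition.
2. Reword the linkage-measure sentence to that denominator.
3. Keep linkage among positives, and the number of positives per arm, as descriptive figures.
4. For participants lost to follow-up, keep the plan's approach ("Multiple imputation (MI) methods will be applied to address missing values under the missing at random (MAR) assumption") and its sensitivity analyses. Vary the assumption in both directions, since unequal capture could favour the app. State how Fisher's test is combined with imputed data.
5. State which arms the 25 to 40 expected positives cover, and the basis for the figure.

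The cost is a revision of the analysis text, including a decision on the exact test under imputation. No new data or participants are needed, and the low-power statement should stay.
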